
cost of surgery and aftercare in surgical patients, we believe that this project will establish the ground-work necessary to develop a sustainable clinical program for other surgical practices to minimize post-surgical complications and overall costs.

2. Objectives (include all primary and secondary objectives)

1. Evaluate whether an intensive pre- post-surgical smoking cessation intervention will promote smoking cessation both pre- and post-surgery.

Hypothesis: An intensive smoking intervention will promote smoking abstinence across the pre- and post-surgical phases. Secondary outcomes will include cessation at 1-month postsurgical follow up and other smoking-related outcomes (withdrawal, craving).

2. Assess whether changes in smoking are associated with surgical recovery outcomes.

Hypothesis: Patients who show longer periods of sustained smoking abstinence pre- and post-surgery will have better recovery post-surgery as evidenced by the following outcomes: shorter length of stay, fewer admissions to the ICU, lower total cost of procedure, smaller total quantity of opioid analgesic use, and lower 30-day hospital readmission rates.

3. Examine baseline decision-making characteristics, including smoking motivation, delayed discounting, and distress tolerance, as predictors of post-surgical recovery and smoking cessation outcomes.

Hypotheses: (1) Patients with strongest positive and negative reinforcement-based smoking motives (i.e., patients whose motives to smoke center around experiencing the positive outcomes of smoking, such as mood enhancement and/or ameliorating the cons of abstaining from smoking, including craving and negative affect) will be most likely to resume smoking post-surgery. (2) Patients with steeper discounting curves at study baseline and/or lower distress tolerance will be less likely to abstain from smoking pre-surgery, may request higher quantities of opioid analgesics post-surgery, and will be at the greatest risk of relapsing to smoking post-surgery.

The overall objective of this study is to assess the feasibility of conducting a pre-postoperative smoking cessation study in presurgical patients. If a positive signal is found, then these data will be used to support a large-scale grant application to evaluate this approach using a randomized, controlled study design.

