Ultimately, this study will provide a unique, innovative contribution to the literature because it will be the first to promote both pre- and post-surgical smoking cessation, it will layer varenicline, counseling, and motivational incentives to produce large magnitude effects, it will evaluate decision-making characteristics at baseline that may impact postsurgical decisions to either maintain smoking abstinence or reinstitute smoking, and it will focus on surgical recovery outcomes and rates of opioid analgesic use, as well as smoking cessation. The researchers are uniquely poised to conduct this research. [name] has run two incentive-based smoking cessation trials in treatment reticent smokers (Dunn et al., 2008; Dunn et al., 2010), and has worked on two studies administering varenicline for treatment purposes, including an R21 funded study awarded to Co-I [name] and conducted here (IRB protocol NA_00074143).

Pilot Data: Post-Surgical Costs and Smoking Status.

We also have data to support our proposal. Table 1 presents data from the Bayview Medical Hospital, collected from all patients in FY14. Among patients seeking voluntary bariatric surgery, 5% were rated as *current*

Table 1.	Smokers N=23	Nonsmokers N=451	P-Value
Bariatric Surgery Patients (2014)			
Length of Stay (Days)	8.2	3.5	0.005
Total Cost (\$)	34,781.90	21,405.19	0.024
Total Cost in Meds (\$)	1,364.66	520.68	0.064
30-day Readmission (%)	17%	4%	0.018

smokers (a total of 23 individuals overall). Despite this large discrepancy in sample size, several variables emerged as being significantly different between the smoker and nonsmoking patients, including the overall length of hospital stay, total cost of the procedure, and likelihood of 30-day readmission. These data indicate a positive signal exists that warrants additional research attention, and provides evidence that there will be sufficient sample size from which to recruit for a pilot project. **The total savings (\$14,220.69) between the smoker and nonsmoker groups, regarding total cost and total cost of meds, is enough money to pay 21 participants or to completely run 9 participants.** Please note: Based on population

prevalence alone, we believe this clinical data, likely underestimates the true rate of current smokers among presurgical patients. Many are likely to temporarily quit based on the advice of their surgeons and without any evidence-based intervention in place, relapse rates are likely to be very high.

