Following the surgery, patients will resume weekly study visits approximately two weeks post-surgery in order to continue with the post-surgical varenicline administrations and to assess post-surgical recovery and smoking cessation outcomes. We will attempt to coordinate with the surgery team to schedule patients' first post-surgical study visit on the same day as their two-week post-surgical follow-up visit with their surgeon

in order to maximize convenience for patients, and participants will be given a 2-week supply of varenicline at the study visit immediately prior to their scheduled surgery so that they can continue taking the full dose while recovering from surgery. Patients will return weekly for a total of six post-surgical study visits. Additional follow-up may occur for six months post-intervention. More details about timing of each of the intervention components are listed below:

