2. Varenicline: Varenicline will be administered as clinically indicated and will begin approximately 4-6 weeks prior to surgery. All participants will receive a 1-week dose induction period (0.5mg QD Days 1-3, 0.5mg BID Days 4-7) before transitioning to a full maintenance dose (1mg BID). The target-quit date (TQD) will be on Day 8 (week 2) and will coincide with the 1st day of the maintenance dose, consistent with recommended guidelines. Participants will receive a 1-week supply of varenicline (with 3 days of extra doses in the event of an unpredicted event) in blister packs at each study visit. This will enable us to better track medication adherence and adverse events, and will help encourage participants to attend weekly visits. There is nothing experimental about the use of varenicline in this study. Participants will receive a 2-week supply of varenicline (with 3 days of extra doses) at the visit immediately prior to the participants’ scheduled surgery in order to allow participants to continue taking the full maintenance of varenicline uninterrupted, while also allowing for ample healing time before returning for the first study visit post-surgery.

3. Incentives: Incentive payments will begin on the TQD (week 2) and will be in place for 5 weeks or until surgery (whichever is sooner). Participants will receive monetary based incentives for biochemical evidence of smoking abstinence. Abstinence will be determined via breath carbon monoxide (CO) ratings during Week 2, and via urinary cotinine for the duration of the study. The transition from CO to cotinine is a common procedure that provides a method for awarding incentives to participants who have recently begun abstaining from smoking but will still test positive for cotinine (because of the long elimination half-life of cotinine). Cotinine-based testing will be used as the definition of abstinence during weeks 3-12. CO will be tested using mobile meters and abstinence will be

Table 2. Incentive and Compensation Structure

Study Week	Study Visit	Incentives	Visit Payments
Screening			\$30
1	-6		\$20
2	-5	\$20	\$20
3	-4	\$40	\$20
4	-3	\$60	\$20
5	-2	\$80	\$20
6	-1	\$100	\$20
7	1		\$50
8	2		\$60
9	3		\$70
10	4		\$80
11	5		\$90
12	6		\$100
Follow-up			\$50
Total:		\$300	\$650

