- b. Justification and safety information if FDA approved drugs will be administered for non-FDA approved indications or if doses or routes of administration or participant populations are changed.

N/A

- c. Justification and safety information if non-FDA approved drugs without an IND will be administered.

N/A

8. Study Statistics

Outcome Measures: We will collect a variety of outcome measures to enable a full characterization of decision-making factors at baseline, and the impact of this intervention on smoking status, postsurgical outcomes, opioid analgesia utilization, and cost.

- a. Primary outcome variable.

Smoking Outcomes: Our primary outcome variable will be smoking status. Smoking abstinence will be defined as a negative biochemical sample + self-report of no smoking for the past 7 days, mean % negative samples, and mean continuous negative samples. Smoking will be evaluated within each pre and post-surgical phase, and collapsed over the 11-week targeted cessation period (following the TQD during week 2). Point prevalence smoking abstinence at the follow-up will be defined as a negative cotinine sample + self-report of no smoking for the past 7-days.

b. Secondary outcome variables.

Secondary smoking outcomes will include ratings of nicotine withdrawal and craving, using standardized measures, and frequency of adverse events judged to be related to varenicline or smoking cessation.

Surgical Recovery Outcomes: A variety of postsurgical outcomes will be evaluated. These will include length of hospital stay, overall quantity and frequency of opioid analgesic use, pain ratings of during the recovery period, types and frequency of post-operative complications, frequency of admission into the intensive care unit, and 30-day hospital readmission rates.

c. Statistical plan including sample size justification and interim data analysis.

Since this is an open-label study design, results will be analyzed in a mostly descriptive method.

Smoking Outcomes: Smoking outcomes will be evaluated as a function of time over the 11-week intervention. Smoking cessation rates will also be compared from the pre to post-intervention phases.

Surgical Recovery Outcomes: Surgical outcomes will be evaluated as a function of percent biochemically-confirmed smoking abstinence, to assess whether the duration and/or magnitude of smoking abstinence is statistically associated with 30-day readmission rates, opioid analgesic use, and other surgical outcomes.

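### Section 8.c relates surgical recovery only to percent abstinence with no phase named, so it does not measure the sustained duration that Objective 2 asks about

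*Combined protocol and SAP*

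**What the plan says.** The hypothesis under Objective 2 (Section 2) is about duration: "Patients who show longer periods of sustained smoking abstinence pre- and post-surgery will have better recovery post-surgery".

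For the analysis, Section 8.c says: "Surgical outcomes will be evaluated as a function of percent biochemically-confirmed smoking abstinence, to assess whether the duration and/or magnitude" of abstinence is associated with readmission, opioid use and other surgical outcomes. It gives no phase or denominator for the percent.

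Section 8.a offers more for the smoking outcomes. Its abstinence summaries include "mean % negative samples, and mean continuous negative samples", and it sets the windows: "Smoking will be evaluated within each pre and post-surgical phase, and collapsed over the 11-week targeted cessation period". Section 8.c does not say which of these summaries or windows applies to the surgical outcomes.

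Two points of timing in Section 5.a matter:

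- **Start of treatment.** "Varenicline will be administered as clinically indicated and will begin approximately 4-6 weeks prior to surgery", with the quit date on Day 8. The same section also describes a start about six weeks ahead with six weekly pre-surgical visits, and Table 2 is laid out that way.
- **Visits after surgery.** "patients will resume weekly study visits approximately two weeks post-surgery", and "Patients will return weekly for a total of six post-surgical study visits".

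**The concern.** Percent abstinence and sustained duration are different quantities. Percent does not distinguish a run that lasts up to surgery from scattered negative samples, or from an early run that ends in relapse before the operation. Among full abstainers it carries no information on how long they abstained. The background (Section 4) treats length as important: it puts the benefit at four weeks of pre-surgical abstinence and says that longer is better.

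The missing phase raises a question of time order. Length of stay, ICU admission and in-hospital opioid use are usually settled before the first post-surgical sample. An exposure that includes later samples would partly describe behaviour that follows the outcome, and that behaviour may be affected by how recovery went. Leaving the window open also allows it to be chosen after the data are seen.

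What is at stake is how well the pilot answers Objective 2 and informs the randomized trial it is meant to support. The cessation outcomes are not affected.

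**Working it through.** **1. The plan's own figure.** Twelve weeks with the quit date on Day 8 gives 12 × 7 − 7 = 77 days = 11 weeks, which matches the cessation period in Section 8.a.

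**2. Pre-surgical window.** Days from quit date to surgery = 7 × (weeks from start to surgery) − 7. I assume one scored sample per weekly visit from the quit date.

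| Start before surgery | Window | Scored samples |
|---|---|---|
| 6 weeks (nominal: Section 5.a, Table 2) | 35 days | 5 |
| 5 weeks | 28 days | 4 |
| 4 weeks | 21 days | 3 |

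Section 6 requires surgery to be 5-10 weeks ahead, so the 21-day case needs some delay between screening and first dose.

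**3. Percent against duration.**

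- 3/3, 4/4 and 5/5 all score 100%, for 21, 28 and 35 days.
- A participant on the nominal schedule who quits a week late and then sustains scores 4/5 = 80% with 28 days. That ranks below 3/3 = 100% with 21 days.
- With five samples, three negative scores 60% whether they are the last three (a three-week run up to surgery) or the first three (no run at surgery).

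**4. If the percent pooled both phases.**

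- Six post-surgical samples make up 6/11 = 55%, 6/10 = 60% or 6/9 = 67% of the total.
- The first falls at about day 14. The mean stay of smokers in Table 1 (bariatric patients only) is 8.2 days, so the first sample comes about 14 − 8.2 = 5.8 days later.
- A participant negative at 5/5 before surgery and 0/6 after scores 5/11 = 45%.
- One negative at 0/5 before and 6/6 after scores 6/11 = 55%.

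**5. Size under assumed behaviour.** These are simulations of 400,000 draws. The behaviour patterns are assumptions and do not come from the documents.

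- *Quit once and sustain.* The abstinent fraction is uniform, or 60% full with the rest uniform, or 60% full and 40% none. Start times vary between 4 and 6 weeks. Pre-surgical percent correlates with abstinent days at about 0.87 to 0.99. With every start fixed at six weeks the correlation is 1.
- *Weekly lapses.* The chances of being abstinent in the first week, staying abstinent and returning to abstinence are (0.6, 0.85, 0.25), (0.5, 0.8, 0.4) or (0.7, 0.9, 0.3). Pre-surgical percent correlates with the unbroken run up to surgery at about 0.77 to 0.84. Pooled percent correlates with it at about 0.58 to 0.70, or 0.53 to 0.65 if an unsampled week follows surgery.
- *Same lapses, every start fixed at six weeks.* The results are 0.77 to 0.84 pre-surgical and 0.60 to 0.70 pooled (no unsampled week), almost unchanged.

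Suppose the outcome depends on percent only through unbroken days, with a true correlation of 0.50. The observed correlation is then 0.50 times the figures above:

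- quit once: 0.50 × 0.87 = 0.435, up to about 0.50;
- lapses, pre-surgical percent: 0.50 × 0.77 = 0.385 to 0.50 × 0.84 = 0.42;
- lapses, pooled percent: 0.50 × 0.53 = 0.265 to 0.50 × 0.70 = 0.35.

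**6. Precision at n = 20.** By Fisher's transformation with standard error 1/√17, the 95% interval is about 0.07 to 0.77 for r = 0.50 and −0.17 to 0.65 for r = 0.29.

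**The case against.** **Section 8.a already covers this.** It defines a continuous measure and both phases, and in a short, mostly descriptive section 8.c might be read as drawing on them. This stands in part, and it is why the repair is small. But 8.a assigns those definitions to the smoking outcomes, and 8.c names percent alone.

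**The varying window matters little.** This stands. A reader might infer that the 21 to 35 day spread is the main problem. The schedule is nominally six weeks, and fixing every start at six weeks leaves the lapse correlations almost unchanged. The larger losses come from assumed lapses and from pooling.

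**The 45% versus 55% reversal needs pooling.** This also stands. A reader might infer that the plan ranks patients who smoked up to surgery above those who abstained. Section 8.c does not say that it pools, and the example takes an extreme participant. It shows only why the phase should be named.

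**Twenty completers cannot separate the two exposures.** True: the intervals overlap almost entirely. A descriptive analysis still needs an exposure that matches its hypothesis and precedes the outcome.

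**A run measure is fragile.** This stands. Section 5.a cites strip specificity of 92% to 97.6%. Over four cotinine samples, if errors are independent, a true abstainer has a 1 − 0.976⁴ = 9% to 1 − 0.92⁴ = 28% chance of at least one false positive, which would cut the run. Percent would lose only one sample. The fix therefore keeps percent and adds a tolerant version of the run.

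**Conclusion.** The point holds as a cheap improvement. Section 8.c sets out to assess duration but names an exposure that does not measure sustained duration, and it leaves open whether samples taken after the in-hospital outcomes count towards it.

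The effect is small if participants quit once and stay quit. It is moderate if lapses are common, and larger if phases are pooled. These sizes rest on assumed lapse rates and on taking the unbroken run up to surgery as the exposure that matters. The timing argument assumes stays shorter than about two weeks, for which Table 1 gives only a bariatric mean.

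A reader might infer that the Objective 2 analysis, or the pilot, is invalid. The documents do not support that. The aim is feasibility, the plan is mostly descriptive, and without a control arm neither exposure could show cause.

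**What to change.** Add to Section 8.c:

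1. Alongside percent, use the continuous measure from 8.a as a duration exposure: consecutive negative samples, with smoke-free Timeline Follow-Back days, running up to surgery. Show a sensitivity version that allows one isolated positive sample with no self-reported smoking.
2. For length of stay, ICU admission, in-hospital opioid use, complications and 30-day readmission, take the main exposure from the pre-surgical phase only. Readmission belongs here because its window overlaps visits from about day 14. Show post-surgical abstinence separately, as description.
3. Report days from quit date to surgery for each participant.
4. Have the first post-surgical Timeline Follow-Back cover every day since the last pre-surgical visit.

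Start dates, eligibility and the cessation outcomes stay as they are.

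**Cost.** A few sentences, a little more analysis and a slightly longer recall at one visit, with no extra visits or participants. The run measure is sensitive to a single false-positive strip and to slow cotinine clearance in late quitters. Days after the last pre-surgical sample rest on self-report. Duration also depends partly on surgical scheduling, which is why percent is kept.

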Study Visits: Participants will attend an initial in-person screening visit, described above, and will return to the clinic on approximately a weekly basis during study weeks 1-12 to receive the intensive pre- post-surgical smoking cessation intervention. Visits during the surgical week will occur prior to the surgery to allow for postsurgical recovery time and we will provide 2 weeks of medication at that visit to allow participants to continue using the medication during their recovery period and provide general flexibility to participants who are unable to complete a visit during their first postsurgical week. Each visit will include collection of a urine sample (that will be tested for urinary cotinine and illicit drug use), a breath CO sample, and self-report questionnaires. None of the data collected during study visits will be shared with the patients' surgical team. Participants will be contacted via phone approximately 3 weeks after study

completion and asked whether they are still abstaining from smoking. Those who endorse continued abstinence will be asked to complete a follow-up visit, during which they will provide a urine sample that will be tested for evidence of cotinine. Participants may be contacted over an additional six month period for follow-up questions pertaining to treatment outcome. Participants will be compensated for attending study visits and completing brief questionnaires and tasks; session payment values will escalate after surgery to encourage continued retention (a standard practice in our treatment protocols) and the total possible study visit compensation will be \$650.

- c. Blinding, including justification for blinding or not blinding the trial, if applicable.

Given that this is an open-label pilot study, all participants will receive the same intensive pre to post-surgical smoking cessation intervention in order to collect the data necessary to illustrate the feasibility of incorporating such an intensive intervention into the hospital setting. This pilot data will be used to support the need for future funding to complete larger randomized controlled trials, and/or multi-site trials. Given that no comparison condition is being included in the current pilot study, the issue of blinding is not applicable at this time.

- d. Justification of why participants will not receive routine care or will have current therapy stopped.

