There is no standard and/or routine access to smoking cessation in elective surgical patients. This study will not disrupt any ongoing routine care associated with the participant's surgery.

- e. Justification for inclusion of a placebo or non-treatment group.

N/A

- f. Definition of treatment failure or participant removal criteria.

Participants failing to continue to meet any of the inclusion/exclusion criteria will be removed from the study and an appropriate clinical referral provided. For example, subjects developing a psychiatric disorder or symptoms requiring treatment (e.g., mania, suicidality, and psychosis), major medical illnesses or serious injuries, which would preclude further participation, will be withdrawn. Subjects who consistently fail to show up for the first treatment session may also be withdrawn.

- g. Description of what happens to participants receiving therapy when study ends or if a participant's participation in the study ends prematurely.

Participants will be debriefed after completing the 1-month follow-up, 6-month follow-up, or premature removal. They will be fully informed about all treatment options for smoking cessation and provided with additional referrals as needed. Any participant who is discharged or voluntarily leaves the study will be provided referrals for obtaining assistance with smoking cessation. The participants will continue meeting with their surgical team, consistent with routine practice for post-surgical patient care and independent of the study.

6. Inclusion/Exclusion Criteria

Inclusion Criteria: We will recruit cigarette smokers who have scheduled an elective surgery to participate in the study. Inclusion criteria will include having a surgery scheduled 5-10 weeks in advance, reporting regular cigarette smoking (smoking 3 times a week or more) and providing a cotinine-positive urine sample.

Exclusion Criteria: Exclusion criteria will include being contraindicated for varenicline use, using products other than cigarettes as a primary nicotine product (including e-cigarettes), providing an illicit drug-positive urinalysis test without evidence of concurrent prescription (e.g., for narcotic pain medications, for example), being pregnant or breastfeeding, or a score >20 on the Beck Depression Inventory-II or a score ≥ 0 on the suicide question of the BDI, past year suicidal ideations or behavior on the C-SSRS, being

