Study-related Measures: We will generate summary scores for each of the study measures and evaluate whether baseline values were positively associated with smoking outcome, and whether there were any changes in measures over time as a function of smoking status. These data will be used to help identify which measures may be most sensitive to change over time for a full-scale trial.

Sample Size Considerations: Our proposed sample of 20 completers is consistent with other open label studies of this kind. Additionally, our pilot data on bariatric patients from FY 2014 included only 23 smokers and still provided enough power to show a signal regarding the effects of smoking status on duration of hospital stay, total costs, and 30-day hospital readmissions. As such, we believe 20 completers will be a large enough sample to demonstrate an effect of the intensive intervention on promoting smoking cessation and minimizing post-surgical complications, and will also be a feasible sample size to recruit within the 2-year study period.

d. Early stopping rules.

This study will be stopped if we have evidence that enrolling participants into the study puts them at undue risk of experiencing complications during their surgery. We do not anticipate this happening, however since this is the first study of its kind in this population, we will monitor the data closely to verify safety of the participants.

9. Risks

a. Medical risks, listing all procedures, their major and minor risks and expected frequency.

Varenicline Administration:

Side-effect risks associated with varenicline administration (21): Allergic reactions to varenicline can be life-threatening and are generally characterized by a swelling of the face, mouth, and throat that can cause trouble breathing. *GI*: Nausea is the most frequent side-effect of varenicline and is present in approximately 30% of participants taking varenicline (versus 10% of participants taking placebo). The nausea associated with varenicline is generally transient, dose-dependent, of moderate intensity, and leads to dose discontinuation in only 3% (0.6% - 9%) of people who begin taking varenicline. Constipation, flatulence, and vomiting are more rare but possible side-effects. *Sleep complaints*: Insomnia (12% in

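### Section 8c credits 20 completers with showing an intervention effect on post-surgical complications, which a smokers-only design with no comparator or benchmark complication rate cannot show

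*Combined protocol and SAP*

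**What the plan says.** Section 8c (Sample Size Considerations) gives three grounds for the sample: similarity to other open-label studies, a pilot, and recruitability within two years. On the pilot it says "our pilot data on bariatric patients from FY 2014 included only 23 smokers and still provided enough power to show a signal", naming hospital stay, total cost and 30-day readmission. It then draws the inference that "20 completers will be a large enough sample to demonstrate an effect of the intensive intervention on promoting smoking cessation and minimizing post-surgical complications". It gives no significance level, power, effect size or test.

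The pilot is in Section 4 (Background, Table 1): 23 smokers and 451 nonsmokers, all bariatric patients. The text there says "Despite this large discrepancy in sample size, several variables emerged as being significantly different between the smoker and nonsmoking patients". The table lists length of stay, total cost, medication cost and 30-day readmission (17% against 4%, p = 0.018). It has no row for complications.

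On the design of this trial, Section 6 says "We will recruit cigarette smokers who have scheduled an elective surgery to participate in the study", and Section 5c says that "no comparison condition is being included in the current pilot study". Section 8b lists post-operative complications as a secondary outcome, without an expected rate. Under Surgical Recovery Outcomes, Section 8c says "Surgical outcomes will be evaluated as a function of percent biochemically-confirmed smoking abstinence".

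**The concern.** A sample-size statement should say what the planned number of patients can show under the planned analysis. Here the number is supported by a different comparison, on different outcomes, in a narrower population. The pilot's ability to detect a difference came from a contrast with 451 nonsmokers, and nothing in this trial takes their place.

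The sentence also sets up a conclusion. Section 2 says that a positive signal will be used to support a large grant application for a randomized trial. If Section 8c stands, an association between abstinence and recovery among about 20 patients could be put forward as an effect of the intervention on complications. Patients who manage to abstain may differ from those who do not in ways that also affect recovery, so the association does not estimate that effect.

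**Working it through.** **1. The plan's own figure.** The number 20 cannot be reproduced, because Section 8c gives no inputs for it. The one pilot figure that can be checked is the readmission p-value. With 23 smokers, 17% is 4/23. With 451 nonsmokers, a rounded 4% is 16 to 20 events.
- Fisher's exact test, 4/23 against 18/451: p = 0.0172.
- Fisher's exact test, 4/23 against 19/451: p = 0.0202.
- Chi-square with continuity correction, 4/23 against 19/451: p = 0.0177.

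The stated 0.018 is consistent with these. The pilot figure is not in dispute.

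**2. Pilot and trial side by side.**

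| | Pilot (Section 4, Table 1) | This trial |
|---|---|---|
| Contrast | 23 smokers against 451 nonsmokers | None between groups; achieved percent abstinence within the sample (8c) |
| Patients | Bariatric surgery | Smokers having elective surgery generally (6) |
| Outcome | Stay, costs, readmission | Complications claimed (8c); no rate given |
| Comparator or benchmark | 451 nonsmokers | No comparison condition (5c); no benchmark complication rate |

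On each row the pilot differs from what the conclusion needs. The third row also means that power for complications cannot be calculated from the documents.

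**3. Illustration with the only event rate in Table 1.** Assumptions that are mine: the planned association is reduced to two groups; the 20 patients split into 8 smoking and 12 abstinent (Section 4 cites short-term cessation as high as 60%, and 0.60 × 20 = 12); the true readmission rates are 17% and 4%; and the test is Fisher's exact, two-sided 5%.

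Power is the sum, over all tables with p ≤ 0.05, of Bin(x; 8, 0.17) × Bin(y; 12, 0.04).
- With y = 0, significance needs x ≥ 3 (3/8 against 0/12 gives p = 0.049).
- P(x ≥ 3) = 0.141 and P(y = 0) = 0.613; the product is 0.0865.
- The remaining tables, mainly x ≥ 5 with y = 1, add about 0.0016.
- Power = 0.088, or about 9%.

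For the other splits tried, from 4 smoking/16 abstinent to 14/6, exact power runs from 0.1% to 8%. The same rates at 23 against 451 give exact power of 60%, and 20 against 451 gives 56%. Because these use the pilot's observed rates, they are not independent evidence about the pilot. They show only that its sensitivity depended on the large nonsmoker group.

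**4. What a low count in 20 would establish.** Expected readmissions are 20 × 0.17 = 3.4 at the smokers' rate and 20 × 0.04 = 0.8 at the nonsmokers' rate. Exact (Clopper-Pearson) 95% upper limits:
- 1/20: 24.9%, which does not exclude 17%.
- 0/20: 16.8%, which only just falls below 17%.

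The 17% is itself imprecise: 4/23 has an exact 95% interval of 5% to 39%.

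**5. What 20 patients can deliver.** Exact 95% intervals for a cessation rate:
- 12/20 = 60%: 36% to 81%.
- 4/20 = 20%: 6% to 44%.

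**The case against.** The strongest reply is that the documents already limit their own ambition. Section 2 makes feasibility the overall objective and leaves evaluation to a later randomized trial. Section 5a (Screening) asks only whether a signal exists. Section 8c says that "results will be analyzed in a mostly descriptive method" and describes the surgical analysis in terms of statistical association. The disputed sentence is worded as a belief, complications are secondary, no decision rule depends on it, and 20 also rests on precedent and recruitability. All of this stands, and it limits the harm. It does not rescue the sentence, because precedent and recruitability support 20 as a feasible number and say nothing about demonstrating an effect on complications.

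A second reply is that the pilot smokers' 17% readmission, from the same hospital, could serve as an informal reference. The plan never names it as one. It is readmission rather than complications, and it comes from bariatric patients only.

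A third is that the power figure rests on an assumed split. That is correct, and it is offered only to show scale.

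A reader might go further and infer that 20 is too few and must be raised, or that cessation will be reported among completers only. The documents support neither. Twenty is defensible for feasibility, and completing 20 people is stated as a target, not as an analysis population.

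**Conclusion.** The justification is wrong as written in one respect: the step from the pilot to a demonstrable intervention effect on complications. This rests on the text of Sections 4, 5c, 6 and 8c and needs no numerical assumption. With only treated smokers, no comparator and no benchmark complication rate, the study cannot show such an effect.

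The size of the gap can only be illustrated: about 9% exact power for readmission under the assumed 8/12 split, with 17% and 4% taken as true. The lack of a comparator is the main defect, and no power figure measures it. The sample size, the design and the exploratory surgical associations are not in question. The correction is worth making because Section 8c sets out what 20 completers are expected to show, and a grant application may draw on it.

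**What to change.** In Section 8c (Sample Size Considerations):

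- Delete the inference from the 23-smoker pilot and the claim about complications.
- State that 20 completers is a feasibility size chosen on precedent and recruitability.
- Give the precision it delivers for a cessation rate, using intervals such as those in step 5 of the working.
- State that associations of surgical outcomes with percent abstinence are exploratory, will be reported as estimates with 95% confidence intervals, and are not evidence of an intervention effect on complications.

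This adds no patients, visits or data collection, and 20 is unchanged. The cost is that the stated justification becomes less favourable.
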